3.5 Changes to the Analysis from the Protocol

Summary of physical examination will not be presented as specified in sections 8.4.2 and 8.4.3 of the protocol as results are not collected unless they appeared as Clinical significance, in which case they are entered as an AE.

Percent change from baseline in hand PGA and foot PGA at Weeks 4, 8, 12, 16, and 32 will not be present as specified in section 3 of the protocol.

PPD	STATISTICAL ANALYSIS PLAN, Version Final 1.0
Protocol Number: ASN002AD-202 V6.0	Sponsor: Asana BioSciences, LLC

Subgroup analysis by PGA strata at baseline (3 vs. 4) will be performed on the primary endpoint (percent change in mTLSS) and key secondary endpoint (proportion with reduction in PGA) as specified in sections 13.1 and 13.2.

Subgroup analysis by baseline description of CHE (hyperkeratotic, fingertip or pompholyx) will be performed on the primary endpoint (percent change in mTLSS) and key secondary endpoint (proportion with reduction in PGA) as specified in section 13.3 for exploratory purpose.

Validated Investigator Global Assessment (for subjects with AD only) will be analyzed as specified in Section 13.3 for exploratory purpose.

The pruritus score portion of the mTLSS will also be analyzed for exploratory purposes as described in Section 13.3.

All secondary efficacy endpoints will be up to Week 16 (Part A). All secondary efficacy endpoints data after week 16 (after the Placebo patients have crossed over to ASN002) will be considered exploratory efficacy endpoints and will be presented using descriptive statistics.

All exploratory efficacy endpoints specified in section 3 of the protocol, will be summarized by all visits with assessment scheduled from Weeks 4 to Week 32 as specified in section 13.3, instead at Weeks 4, 8, 12, 16, and 32.

In section 9.3.2 of the protocol, Holm's step-down procedure adjustment was proposed to adjust for the two comparisons of interest (40mg vs. Placebo and 80mg vs. Placebo). It is well known that the Hochberg method is optimal than Holm's adjustment. Therefore, Hochberg adjustment will be used for the multiple dose/treatment comparisons. The decision for this changed was made before the unblinding. Since this change would not affect the conduct of the trial in any sense, no protocol amendment was made to account for this change.

4 POPULATIONS FOR ANALYSIS

4.1 Modified Intent-to-Treat Population

This population will include all subjects who received at least one dose of the study product. All subjects will be analyzed according to the treatment group to which they were randomized. The mITT population will be used as the primary analysis population for efficacy.

PPD	STATISTICAL ANALYSIS PLAN, Version Final 1.0
Protocol Number: ASN002AD-202 V6.0	Sponsor: Asana BioSciences, LLC

4.2 Per-Protocol Population

This population will include all subjects who were randomized, who received at least one dose of study product, with no major protocol deviations, and who provided evaluable data for the primary endpoint at Week 16. All subjects will be analyzed according to the treatment group that they actually received during Part A.

The protocol deviations will be presented in a listing and summarized by category. Upon sponsor's review, the listing will also include a flag indicating whether each deviation is considered important or not. Important deviations will be interpreted as major and will result in excluding the related subject from the Per-Protocol Population. This exercise will be done prior to the database lock, on blinded data.

4.3 Safety Population

The safety population will include all subjects who received at least one dose of the study product. All subjects will be analyzed according to the treatment that they actually received in Part A.

4.4 Pharmacokinetic Population

The Pharmacokinetic (PK) population will include all subjects who received at least one dose of ASN002 and have plasma concentration data.

4.5 Pharmacodynamic Population

The Pharmacodynamic (PD) population will include all subjects who received at least one dose of the study product and have at least one assessment of PD parameters

5 GENERAL CONSIDERATIONS

Formats and layouts of tables, listings, and figures (TLF) will be provided in a separate document (output general layout is described in Appendix 1).

5.1 Sample Size

Assuming a common standard deviation of 39% for the percent change-from-baseline mTLSS, a difference of 25% and 35% between the 40 mg dose vs. placebo and the 80 mg dose vs. placebo, respectively, alpha of 5% (two-sided), 25 patients per group would insure an 80% power to obtain a statistically significant treatment effect (using the general F test in an analysis of variance). Assuming between 25-30% dropout rates, up to 35 patients per group will be included in this study.

PPD	STATISTICAL ANALYSIS PLAN, Version Final 1.0
Protocol Number: ASN002AD-202 V6.0	Sponsor: Asana BioSciences, LLC

5.2 Baseline

Unless otherwise specified, baseline value will be defined as the last non-missing assessment prior to or on the first study treatment application date (including unscheduled assessments) in Part A. If the last non-missing assessment is performed on the same date as the first study treatment and time is not available, the assessment will be considered as baseline, except for adverse events (AEs) and medications starting on the first study treatment dose date which will be considered post-baseline.

5.3 Reference Start Date and Analysis Day

Analysis day will be calculated from the first study treatment date and will be used to show start/end day of assessments or events.

For dates on or after the first treatment date, Analysis Day = Date – First Study Treatment Date + 1

For dates before the first treatment date, Analysis Day = Date – First Study Treatment Date

In the situation where the assessment/event date is partial or missing, analysis day will be missing.

5.4 Windowing Conventions

No Statistical Windows have been proposed for this study:

5.5 Descriptive Statistics

All continuous variables will be summarized by presenting the number of subjects, mean, standard deviation, median, minimum, and maximum. Categorical variables will be presented as frequencies and percentages. Summary tables will be presented by treatment and visit, when applicable.

Change from baseline will be calculated as:

Assessment value at post-baseline visit X – baseline value.

Percent change from baseline will be calculated as:

$$(\text{Assessment value at post-baseline visit X} - \text{baseline value}) / \text{baseline value} \times 100.$$

5.6 Statistical Tests

Unless otherwise specified, all statistical tests will be two-sided and will be performed with a significance level of 0.05. Confidence intervals (CIs) will be two-sided with 95% coverage.

PPD	STATISTICAL ANALYSIS PLAN, Version Final 1.0
Protocol Number: ASN002AD-202 V6.0	Sponsor: Asana BioSciences, LLC

5.7 Handling of Retests, Unscheduled Visits, and Early Termination Data

When retests measurements are done, the retest measurement will be considered for the summary analysis. All data from retest visits will be listed.

For Safety Data, unscheduled measurements will not be summarized in by-visit summary tables or figures. However, data from unscheduled visits will be listed.

Early Termination (ET) visit assessments will be summarized as a separate visit in by-visit outputs.

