4.4 Safety Monitoring criteria for Individual Subject Treatment Interruption/Discontinuation

In the event of an adverse event or laboratory abnormality, individual subject study treatment may be temporarily or permanently discontinued based on the investigator's judgment and preferably

following a discussion with the medical monitor in accordance with the guidelines described in this section.

Treatment may be resumed upon recovery to baseline or mild levels after the condition leading to suspension of dosing resolves, at the discretion of the principal investigator in consultation with the medical monitor. A decision to temporarily discontinue study drug and/or to reinstitute study treatment should be discussed with the medical monitor. The investigator may suspend study treatment at any time, even without consultation with the medical monitor if the urgency of the situation requires immediate action and if this is determined to be in the subject's best interest. However, the medical monitor should be contacted as soon as possible in any case of study drug discontinuation/interruption. Resumption of study treatment after temporary discontinuation should always be discussed with the medical monitor.

Any retreatment should only be considered upon written agreement between the investigator and the sponsor. This information pertaining to interruption or discontinuation of study medication and the reasons for it must be recorded in the case report form.

No dose reductions or modifications are permitted.

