4.4.1 Interruption criteria

A subject who meets either of the below criteria will have the study drug interrupted until laboratory retesting is performed and/or event resolution.

- neutrophils $> 0.5 \times 10^3 / \mu\text{L}$ but $< 1 \times 10^3 / \mu\text{L}$;
- platelet count $> 50 \times 10^3 / \mu\text{L}$ but $< 100 \times 10^3 / \mu\text{L}$;
- lymphocytes $> 0.2 \times 10^3 / \mu\text{L}$ but $< 0.5 \times 10^3 / \mu\text{L}$;
- CPK $> 10 \times \text{ULN}$;
- an infection requiring IV treatment with antiviral, antibiotic, antiprotozoal, antiparasite or requiring oral medications of those longer than 2 weeks;
- AST/ALT $> 5 \times \text{ULN}^*$.

*Decision to restart the medication following any laboratory abnormality described above will be made in consultation with the study sponsor and medical monitor.

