2 STUDY OBJECTIVES AND ENDPOINTS

OBJECTIVES	ENDPOINTS
Primary	Efficacy endpoint:
To evaluate the efficacy of ASN002 in subjects with moderate to severe chronic hand eczema (CHE) based on hand modified Total Lesion Symptom Score (mTLSS)	
 Percent change from baseline in hand mTLSS at Week 16
Secondary	Efficacy endpoints:
To evaluate the efficacy of ASN002 in subjects with moderate to severe CHE.	
 Change from baseline in hand mTLSS at Weeks 4, 8, 12, 16 Percent change from baseline in hand mTLSS at Weeks 4, 8, and 12 Proportion of subjects achieving at least a 2-grade reduction from baseline to clear (0), almost clear (1) or mild (2) in hand PGA at Weeks 4, 8, 12 and 16 Proportion of subjects achieving a hand PGA of clear (0) or almost clear (1) at Weeks 4, 8, 12 and 16 Change from baseline in hand PGA at Weeks 4, 8, 12 and 16

PPD	STATISTICAL ANALYSIS PLAN, Version Final 1.0
Protocol Number: ASN002AD-202 V6.0	Sponsor: Asana BioSciences, LLC

OBJECTIVES	ENDPOINTS
	
 • Change and percent change from baseline in Hand Eczema Severity Index (HECSI) at Weeks 4, 8, 12 and 16 • Time to response relative to baseline (based on hand PGA) • Actual hand Patient Global Assessment (PaGA) at Weeks 4, 8, 12 and 16 • Change from baseline in hand Dermatology Life Quality Index (DLQI) at Weeks 2, 4, 8, 12 and 16 • Change and percent change from baseline in pain visual analog scale (VAS) at Weeks 4, 8, 12 and 16
	Safety endpoints:
To evaluate the safety and tolerability of ASN002 in subjects with moderate to severe CHE	
 • Number of Treatment Emergent Adverse Events (TEAEs) • Number of drug-related TEAEs • Proportion of subjects withdrawing for worsening of their CHE at Weeks 4, 8, 12, and 16 • Changes from baseline in vital signs • Change from baseline in ECG • Change from baseline in safety laboratory tests
	Pharmacokinetic endpoints:
To quantify the plasma concentrations of ASN002 in subjects with moderate to severe CHE	
 • Measurement of plasma concentrations of ASN002 in all subjects receiving ASN002 treatment.
Exploratory	Exploratory endpoints:
To evaluate pharmacodynamic (PD), biomarkers and skin microbiome analysis for evidence of drug activity in subjects with moderate to severe CHE	
 • Change from baseline in PD, biomarkers and skin microbiome analysis at Weeks 4 and 16.

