14.2 Clinical Laboratory

Descriptive statistics will be presented for data related to chemistry, hematology and quantitative urinalysis. Change from baseline values will be presented for each post-baseline assessment. Frequencies and percentages for each result will be provided for qualitative urinalysis data.

Shift tables from baseline to each post-baseline visits describing shifts to abnormality will be provided as well. Only subjects with a baseline result and a result at the specified visit for the parameter will be considered.

Separate listings of all data for chemistry, hematology, urinalysis, serology and pregnancy test will be provided.

In addition, separate listings of data for chemistry, hematology, and urinalysis will be provided for each parameter where a subject had at least one abnormal result.

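### SAP 5.7 lets a laboratory retest taken during a drug hold replace the on-drug value in the by-visit safety tables, and does not say whether its rule on unscheduled data overrides this

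*SAP*

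**What the plan says.** SAP 5.7 has two rules that bear on a repeated laboratory test. The first is general: "When retests measurements are done, the retest measurement will be considered for the summary analysis". The next sentence adds: "All data from retest visits will be listed". The second rule is confined to safety data: "unscheduled measurements will not be summarized in by-visit summary tables or figures". Nothing says which applies to a safety retest done between scheduled visits.

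Protocol 4.4.1 sets hold thresholds for neutrophils, platelets, lymphocytes, CPK and AST/ALT. A subject who meets one "will have the study drug interrupted until laboratory retesting is performed and/or event resolution". Protocol 4.4 adds: "Treatment may be resumed upon recovery to baseline or mild levels after the condition leading to suspension of dosing resolves".

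The affected output is a named secondary safety endpoint in SAP 2: "Change from baseline in safety laboratory tests". SAP 5.5 fixes its content: "All continuous variables will be summarized by presenting the number of subjects, mean, standard deviation, median, minimum, and maximum". SAP 14.2 adds: "Shift tables from baseline to each post-baseline visits describing shifts to abnormality will be provided as well". SAP 14.2 plans no table of worst post-baseline values and no count of subjects reaching a 4.4.1 or 4.4.2 threshold.

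**The concern.** Using the repeat is sensible for eligibility retests at screening or for a spoiled sample. SAP 5.7 is not limited to those cases. The only post-baseline laboratory retest that the protocol describes is the one in 4.4.1, and it answers a different question from the value it follows: whether the subject has recovered with drug stopped. Putting it in the by-visit table replaces an on-drug result with an off-drug one, and only because the on-drug result was bad.

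That replacement depends on the outcome. If the drug lowers counts or raises enzymes, holds fall mainly in the active arms and the laboratory tables understate the difference from placebo. Protocol 9.3.3 rules out inferential statistics on safety variables, so these descriptive tables carry much of the laboratory comparison between arms.

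**Working it through.** The plan gives no figure for this rule, so there is none to reproduce. The check sets the rules side by side and then sizes the effect under stated assumptions.

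**1. Is the retest off drug?** Protocol 4.4.1 places the retest inside the hold, and the decision to restart comes afterwards. Fraction of drug remaining = 0.5^(t / half-life). Protocol 2.1.3 gives a half-life of about 10 h; protocol 2.1.2 gives means of 7.3 to 13.7 h.

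- 48 h after the last dose: 0.5^4.8 = 3.6% (1.0% to 8.8% over the range).
- 72 h: 0.5^7.2 = 0.7% (0.1% to 2.6%).

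A retest a few days into a hold is effectively off drug.

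**2. What happens to the trigger value in the by-visit tables?**

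| Trigger value | If the retest rule governs | If the unscheduled rule governs |
|---|---|---|
| 4.4.1 range, scheduled visit | Replaced by the retest | Stays |
| 4.4.1 range, unscheduled visit | Not tabulated | Not tabulated |
| 4.4.2 range, scheduled visit | Stays (no retest in the protocol) | Stays |

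SAP 5.7 names retest visits and unscheduled visits as separate categories, and 4.4.1 uses the word retesting, so the left-hand column is the natural reading. SAP 5.4 sets no analysis windows, so nothing there limits how late a retest may stand in for a visit.

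**3. Which values are exposed?** For the three blood counts, 4.4.1 is an intermediate band: neutrophils 0.5 to 1, lymphocytes 0.2 to 0.5, platelets 50 to 100 (all x 10^3/uL). Counts at or below the lower bound fall under 4.4.2. For AST/ALT (> 5 x ULN) and CPK (> 10 x ULN), 4.4.1 has no upper bound and 4.4.2 has no entry, so even the highest values are exposed.

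**4. Size for one subject and for the arm mean.** Inputs are the screening limits in exclusion criterion 19, the hold thresholds in 4.4.1, and up to 35 subjects per arm (protocol 9.1). If the retest is at or inside the screening limit, the on-drug change is understated by more than the gap between the two. Assume 3 of 35 subjects are held for one parameter at one visit; the arm mean change is then understated by more than 3 x gap / 35.

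| Parameter | Screening limit | Hold threshold | Gap | 3 x gap / 35 |
|---|---|---|---|---|
| Neutrophils (10^3/uL) | 1.8 | 1.0 | 0.8 (44%) | 0.07 |
| Lymphocytes (10^3/uL) | 0.9 | 0.5 | 0.4 (44%) | 0.03 |
| Platelets (10^3/uL) | 125 | 100 | 25 (20%) | 2.1 |
| AST/ALT (x ULN) | 2 | 5 | 3 | 0.26 |

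CPK has no screening limit, so no gap can be computed.

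**5. Size for shift counts.** Assume 1 to 4 of 35 subjects with a normal baseline have an abnormal trigger value. The table should show 1/35 = 2.9% to 4/35 = 11.4%; with 25 subjects at the visit, 4.0% to 16.0%. It shows 0% if every retest is normal, and an unchanged count if every retest is still abnormal.

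**6. Two illustrations (assumed values).**

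- Neutrophils 0.8, retest 2.0: the arm mean rises by 1.2/35 = 0.03 with one such subject and 4 x 1.2/35 = 0.14 with four, and the 0.8 no longer appears as the arm minimum.
- ALT 6 x ULN, retest 1.5 x ULN: the mean falls by 4.5/35 = 0.13 to 4 x 4.5/35 = 0.51 x ULN and the maximum of 6 is lost. The shift count does not change, because 1.5 x ULN is still above normal.

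**The case against.** The strongest answer is that the safety-specific sentence in SAP 5.7 governs. The Schedule of Events has no retest visit, so a hold retest between visits is off schedule. If that rule prevails, the scheduled trigger value stays and nothing is replaced. The protocol's other laboratory retests are repeats for eligibility, which may be all the retest sentence had in mind. This stands as a possible reading, so it cannot be said that the trigger value certainly drops out. It does not settle the matter, because the retest sentence has no such limit and the two readings give different tables.

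A reader might infer that all the worst laboratory values disappear. The documents do not support that: the lowest blood counts fall under 4.4.2, where no retest is written in. A reader might also infer that minima, maxima and shift counts are lost entirely. That would require full recovery at retest. Protocol 4.4 allows restart at mild levels, 4.4.1 ties the hold to retesting and/or resolution, and SAP 5.7 does not say which of several retests is used.

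Nor is the signal hidden. SAP 14.1 summarises neutropenia, lymphopenia, liver enzyme elevation and CPK elevation as events of clinical interest, together with TEAEs leading to treatment interruption; the latter can capture a platelet hold. All abnormal results are listed. This also stands, with a limit: protocol 8.4.4 makes a laboratory finding an adverse event only if it is judged clinically significant, and an event table does not show how far the value moved.

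Finally, worst-value tables can be called optional in a Phase 2 trial with descriptive safety only. Their absence alone would not be an error. It matters here because nothing else in the laboratory tables recovers a replaced value.

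**Conclusion.** The point holds on the natural reading of SAP 5.7. A scheduled, on-drug value in the 4.4.1 hold range is replaced in the by-visit laboratory tables by a value taken during the hold. The cause is a rule as written, and the missing order of precedence adds to the problem.

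The effect on means is small: about 2 x 10^3/uL for platelets or 0.07 x 10^3/uL for neutrophils with 3 of 35 subjects held. The effect on reported extremes can be large for individual subjects. Shift counts lose 2.9% to 11.4% of an arm only if 1 to 4 of 35 subjects are held and their retests are normal. The hold rates and the degree of recovery are assumptions. The direction, towards understating laboratory change on drug, follows whenever the retest is closer to baseline than the trigger value. The efficacy analyses are not touched by this laboratory rule.

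**What to change.** Before Part A unblinding, so that the rule is not chosen with results in view:

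1. Change SAP 5.7 so that post-baseline by-visit safety tables use the first valid value at the scheduled visit. A retest replaces it only when the original sample was invalid. This also settles which rule takes precedence.
2. Add to SAP 14.2 one Part A table by arm, giving each subject's worst post-baseline value summarised per parameter and the number of subjects reaching each laboratory threshold in protocol 4.4.1 and 4.4.2. Use all scheduled, unscheduled, retest and early termination results.

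The cost is one reworded rule and one extra table. The values are already collected and listed, so no visits, samples or subjects are added.

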3.4 Randomization, Replacement, and Unblinding Procedures

Subjects will be randomized in a 1:1:1 ratio to one of the following treatment regimens:

- Part A: ASN002 40 mg (16-week treatment); Part B: ASN002 40 mg (16-week treatment)
- Part A: ASN002 80 mg (16-week treatment); Part B: ASN002 80 mg (16-week treatment)
- Part A: Placebo (16-week treatment); Part B: ASN002 80 mg (16-week treatment)

Subjects assigned to regimen starting with a placebo in Part A (first 16 weeks) of the study will receive the highest dose of ASN002 (i.e. 80 mg) for the rest of the treatment period (up to Week 32). Subjects who were assigned to ASN002 in the first part of the study will continue on the assigned treatment dose during the second part of the study up 32 weeks of treatment.

Randomization will occur prior to first dosing, at Day 1 visit. The randomization list will be generated using validated software. Randomization will be stratified for the biopsy collection and for the PGA score of '3' (moderate) or '4' (severe) per treatment group. The master randomization list will be kept secured until the study blind is broken. This list will be uploaded into an Interactive Web Response System (IWRS). The investigator or designee will be able to acquire a randomization number for eligible subjects by connecting to the IWRS

This study will be double-blinded. At all times, treatment and randomization information will be kept confidential and will not be released to, the contract research organization (CRO), or the sponsor's study team until database lock of Part A is completed and all safety data has been cleaned and monitored. Investigators, subjects and clinical staff will remain blinded throughout the study.

PPD	STATISTICAL ANALYSIS PLAN, Version Final 1.0
Protocol Number: ASN002AD-202 V6.0	Sponsor: Asana BioSciences, LLC

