6.7 Analysis Presentation

Subjects will be presented in columns according to their treatment assignment in Part A. In the tables presenting Part B data or combined Part A and Part B data, placebo subjects from Part A

PPD	STATISTICAL ANALYSIS PLAN, Version Final 1.0
Protocol Number: ASN002AD-202 V6.0	Sponsor: Asana BioSciences, LLC

crossed over to ASN002 80 mg will be presented in the placebo/ASN002 80mg column. See Appendix 1 for presentation of treatment groups.

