14 SAFETY ANALYSIS

All safety analyses will be conducted using the safety population and will be presented combined except adverse events, which will be presented separately for Part A and Part B. For both parts subjects will be presented by their initial treatment as assigned in Part A.

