Placebo patients from Part A cross over to ASN002 80 mg treatment during Part B. The treatment columns will be presented as ASN002 40 mg, ASN002 80 mg, Placebo crossed-over to ASN002 80 mg and combined ASN002 80 mg (ASN002 80 mg and Placebo crossed-over to ASN002 80 mg combined).

Study Treatment Full Names	Study Treatment Output Names
ASN002 40 mg	ASN002 40mg
ASN002 80 mg	ASN002 80mg
Placebo crossed-over to ASN002 80 mg	Placebo/ASN002 80mg
ASN002 80mg and Placebo crossed-over to ASN002 80 mg combined	Combined ASN002 80mg

3. Combined Output for Part A and B:

Placebo patients from Part A cross over to ASN002 80mg treatment during Part B.

For the analysis by treatment and visit, (ASN002 80mg and placebo/ASN002 80mg will be anchored by the first dose time) and presented as follows.

Study Treatment Full Names	Study Treatment Output Names
ASN002 40 mg	ASN002 40mg
ASN002 80 mg	ASN002 80mg
ASN002 40 mg and ASN002 80 mg	ASN002 Overall
Placebo	Placebo/ASN002 80mg
ASN002 80mg and Placebo crossed-over to ASN002 80 mg combined	Combined ASN002 80mg

PPD	STATISTICAL ANALYSIS PLAN, Version Final 1.0
Protocol Number: ASN002AD-202 V6.0	Sponsor: Asana BioSciences, LLC

Appendix 2: Algorithm for Imputation of Start/End Date of Adverse Events and Prior/Concomitant Medications

Event Start Date Imputation

- Imputation of event end date should be done before imputation of event start date.
- Completely missing: Impute to the first study treatment date.
- Missing day and month: Impute to January 1st, unless year is the same as year of first study treatment dose then impute to the first study treatment date.
- Missing day: Impute to the 1st of the month, unless month and year are the same as month and year of first study treatment dose then impute to the first study treatment date.
- If imputed event start date is after event end date (imputed or not), set the event start date to the imputed event end date.

Event End Date Imputation

- Completely missing (and not flagged as “ongoing”): Impute to the last contact date.
- Missing day and month: Impute to December 31st, unless year is the same as last contact date then impute to the last contact date.
- Missing day: Impute to the last day of the month, unless year and month are the same as year and month of last contact date then impute to the last contact date.

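### Combined Part A and B laboratory, vital-sign and ECG tables get one undated early-termination row, which in the placebo arm mixes values on placebo with values on ASN002 80 mg (descriptive tables only)

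*SAP*

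**What the plan says.** Four parts of the SAP bear on this, and none produces the result alone.

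- **SAP 5.7** makes ET its own visit category: "Early Termination (ET) visit assessments will be summarized as a separate visit in by-visit outputs". It does not mention Part, time or treatment at termination.
- **SAP 14** sets the scope of the safety tables: "All safety analyses will be conducted using the safety population and will be presented combined except adverse events, which will be presented separately" by Part. It also fixes the columns: "For both parts subjects will be presented by their initial treatment as assigned in Part A".
- **SAP 6.7** says that, in tables of Part B or combined data, placebo subjects "crossed over to ASN002 80 mg will be presented in the placebo/ASN002 80mg column".
- **SAP Appendix 1 item 3** (combined output) maps Placebo to the Placebo/ASN002 80mg label and has no placebo-only column. Its one timing rule is that "ASN002 80mg and placebo/ASN002 80mg will be anchored by the first dose time".

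The arm changes treatment at Week 16: "Placebo patients from Part A cross over to ASN002 80 mg treatment during Part B" (SAP Appendix 1). Under Protocol 7.1 an ET visit can follow discontinuation at any time after the first dose. Protocol Table 1 schedules vital signs and laboratory tests in its follow-up/ET column, and an ECG at ET.

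**The concern.** At a scheduled visit the row label identifies the treatment. In the placebo arm, rows up to Week 16 are on placebo (apart from post-dose samples at Week 16) and later rows are on ASN002 80 mg. The ET row carries no week. A placebo-arm subject who left at Week 6 and one who left at Week 26 therefore enter the same mean, the same change from baseline and the same shift count, although one was on placebo and the other on active drug. In the 40 mg and 80 mg columns the treatment is constant, but the row still joins terminations from the placebo-controlled period with terminations from the uncontrolled one.

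Changes in vital signs, ECG and laboratory tests are a named secondary safety endpoint, and ET is the visit for subjects who stop, some of them because of such findings. What is at stake is whether this row can be interpreted, and whether the by-visit summaries contain a Part A placebo reference at ET.

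**Working it through.** **Step 1. Does any rule split the row?**

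| Question | Source | Answer |
|---|---|---|
| Is ET divided by Part, time or last treatment? | SAP 5.7 | No |
| Are laboratory, vital-sign and ECG tables divided by Part? | SAP 14 | No, only adverse events are |
| Which column holds placebo-arm subjects? | SAP 6.7, Appendix 1 item 3 | Placebo/ASN002 80mg |
| Does anchoring by first dose date the ET row? | SAP Appendix 1 item 3 | No; the rule gives no handling for ET |
| Is there a separate Part A safety summary? | SAP 3.4, Appendix 1 item 1, SAP 14 | A Part A layout exists, but SAP 14 sends non-AE safety data to combined presentation, and SAP 3.4 says the cleaning of Part A safety data involves no interim statistics |

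The rules as written therefore give one mixed row. The tables affected are the by-visit summaries and shift tables of SAP 14.2, 14.3 and 14.4.

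**Step 2. The plan's own group size.** SAP 5.1 assumes differences from placebo of 25 and 35 percentage points, SD 39, two-sided alpha 5% and an ANOVA F test. With means 0, 25 and 35, power at 25 per group is 82.5%, and the smallest group size reaching 80% is 24, so 25 is consistent with the stated 80%. Inflating for dropout gives 25/(1 - 0.25) = 33.3, rounded up to 34, and 25/(1 - 0.30) = 35.7, rounded up to 36. The stated 35 lies between them. The version history entry for protocol 6.0 ties the dropout concern to completing 16 weeks of treatment, so 25-30% is taken as the Part A rate.

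**Step 3. Illustrative make-up of the placebo-arm ET row.** Let dA be Part A dropout (25-30%, from the plan) and dB be Part B dropout (not in the documents; 5-30% assumed).

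- ET visits on placebo = 35 x dA
- ET visits on ASN002 80 mg = 35 x (1 - dA) x dB
- Share on ASN002 80 mg = second / (first + second)

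| dA | dB | On placebo | On 80 mg | Share on 80 mg |
|---|---|---|---|---|
| 25% | 5% | 8.75 | 1.31 | 13.0% |
| 25% | 10% | 8.75 | 2.62 | 23.1% |
| 25% | 20% | 8.75 | 5.25 | 37.5% |
| 25% | 30% | 8.75 | 7.88 | 47.4% |
| 30% | 5% | 10.5 | 1.23 | 10.4% |
| 30% | 10% | 10.5 | 2.45 | 18.9% |
| 30% | 20% | 10.5 | 4.90 | 31.8% |
| 30% | 30% | 10.5 | 7.35 | 41.2% |

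The counts assume that every discontinuing subject attends ET and that every Part A completer enters Part B. If attendance were incomplete but equal in the two Parts, the counts would fall and the shares would not change; unequal attendance would change the shares too.

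**The case against.** The case for leaving the SAP alone has several parts.

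- **SAP 5.7 does not itself require pooling.** That is correct. The single row follows only when 5.7 is read with 14, 6.7 and Appendix 1. Under SAP 5 the table layouts are in a separate document, which could split the row. Nothing in the SAP requires it to.
- **SAP 6.7 speaks of subjects who crossed over**, so placebo subjects who left in Part A might be meant to stay out of that column. But SAP 14 assigns columns by initial treatment, and Appendix 1 item 3 offers placebo subjects no other column. On this reading they would have nowhere to go.
- **A reader might infer that safety findings which lead to stopping would be hidden, or could not be compared with placebo.** The documents do not support this. Under Protocol 8.4.1, 8.4.4 and 8.4.5, clinically significant vital-sign, laboratory and ECG findings are recorded as adverse events. SAP 14 and 14.1 present adverse events separately by Part. The SAP 14.1 summary covers events leading to drug or study discontinuation, and events of clinical interest such as neutropenia, anemia and liver enzyme elevation. SAP 14.2 to 14.4 also list all values, and Appendix 1 orders listings by treatment, subject, date and visit, so each ET value can be placed in its Part.
- **The row would still be weak after a split.** It would average terminations at different weeks in a self-selected group, with few subjects, and Protocol 9.3.3 plans no inferential safety statistics. This stands, and is the main reason for a low priority. A split nonetheless removes the mixing of treatments, which is the avoidable part.

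**Conclusion.** The point holds as one of presentation. The SAP's rules, applied together, give one ET row in the combined laboratory, vital-sign and ECG tables. In the placebo arm it averages values on placebo with values on ASN002 80 mg, and in the active arms it joins controlled and uncontrolled periods. Any ET attendance in both Parts produces this. The shares in the table are illustrative: they rest on an assumed Part B dropout and full ET attendance, and should not be read as a forecast.

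Efficacy results, hypothesis tests and adverse-event tables are not affected, and no individual data are lost. Priority: optional, low.

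**What to change.** Add to SAP 5.7:

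> In outputs combining Parts A and B, ET assessments will be summarised in two rows, ET in Part A (before the first Part B dose) and ET in Part B, within the initial-treatment columns of Section 14. For the placebo arm the Part A row is labelled as on placebo and the Part B row as on ASN002 80 mg. Only the Part B ET values of placebo-arm subjects contribute to the Combined ASN002 80mg column.

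Apply it to SAP 14.2, 14.3 and 14.4, and add a matching note to Appendix 1 item 3.

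Two simpler-looking remedies would cause trouble. Regrouping subjects by treatment at termination contradicts the initial-treatment rule in SAP 14. Barring placebo ET values from every column with ASN002 80 mg in its name could leave them with no column in the combined layout.

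The cost is a short SAP addition, the Appendix 1 note, one extra row per table and small counts in each row. No new data are needed.
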